4.2.2 Compliance with the criteria for starting the next treatment cycle

The study drug can be administered only after the results of the examination on the first day before the next treatment cycle confirm that all the criteria listed in the table below are met.

Table 1.1 Conforms to the criteria for starting the next treatment cycle

Hemoglobin values	$\geq 90\text{g/L}$
Neutrophil	$\geq 1.5 \times 10^9/\text{L}$

count	
platelet count	$\geq 75 \times 10^9/L$
serum total bilirubin	$\leq 1.5 \times UNL$
Aspartate transferase	$\leq 3 \times UNL$
Alanine transferase	$\leq 3 \times UNL$
Serum creatinine	$\leq 1.5 \times UNL$
diarrhoea	Compared with baseline, the number of bowel movements per day increased by less than 4 times
Oral mucositis	There was only mucosal erythema without patchy ulceration or pseudomembrane formation
Sensory nerve disorder	Feelings of abnormality or dullness that do not interfere with daily activities

Note: If an adverse reaction other than the above is found that causes a delay in the start of the next treatment cycle, the investigator will determine whether the administration of the next treatment cycle can be started when the adverse reaction is reduced or recovered.
	

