- (1) Histopathology was diagnosed as rectal adenocarcinoma, all other histological types were excluded, and the colonoscopy report or clinical physical examination suggested the presence of hemorrhoids;
- (2) The clinical pathological stage of the tumor is T3-4 or N+ and M0; 8th edition AJCC TNM staging, Appendix 1)
- (3) Immunohistochemical staining of tissue samples showed that YWHAB was highly expressed in rectal cancer patients;
- (4) The age of obtaining informed consent is 18-75 years old;
- (5) Eastern United States Cooperative Group Physical Status Score (ECOG) was 0-1 points (refer to Appendix 3);
- (6) No previous systemic anti-tumor treatment for rectal cancer, including cytotoxic drugs, immune checkpoint inhibitors, molecular targeted therapy, endocrine therapy, etc.;
- (7) Based on the following laboratory test values obtained during the screening period, appropriate organ function is present: white blood cell count $\geq 3 \times 10^9/L$, neutrophil count $\geq 1.5 \times 10^9/L$, platelet count $\geq 75 \times 10^9/L$, serum total bilirubin $\leq 1.5 \times$ upper limit of normal (UNL), aspartate aminotransferase or alanine aminotransferase $\leq 2.5 \times$ UNL, serum creatinine $\leq 1.5 \times$ UNL;
- (8) Women of childbearing age must have a negative serum pregnancy test within 3 days prior to the start of study medication and be willing to use a medically recognized effective contraceptive method (e.g., IUD, pill, or condom) during the study and for 3 months after the last dose of study medication;

- (9) For male subjects whose partner is a woman of reproductive age, effective contraception was used during the study and for 3 months after the last study dose;
- (10) The subject has given his/her own consent and signed an informed consent form, and the subject is willing and able to comply with the planned visits, research treatment, laboratory tests and other trial procedures.

3.2 Exclusion criteria:

- (1) Whole body CT, MR or PET-CT (at least including chest, whole abdomen and pelvis) confirmed distant metastasis;
- (2) Whole genome testing for DPD enzyme deficiency or 7/7 homozygotes for UGT1A1*28 locus in patients;
- (3) The patient has complete intestinal obstruction, active bleeding or perforation and requires emergency surgery;

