- (4) Previous or concurrent presence of other active malignancies (excluding malignancies that have been treated curatively and have not recurred for more than 5 years or carcinoma in situ that can be cured by adequate treatment);
- (5) Having had a thrombotic or embolic event, such as a cerebrovascular accident (including transient ischemic attack), pulmonary embolism, or deep vein thrombosis, within 12 months prior to enrollment;
- (6) In the 12 months prior to enrollment, the following conditions occurred: myocardial infarction, severe/unstable angina, NYHA class II or higher heart failure, clinically significant supraventricular or ventricular arrhythmias, and symptomatic congestive heart failure;
- (7) Systemic use of antibiotics for more than 7 days within 4 weeks prior to enrollment, or unexplained fever >38.5°C during screening/ prior to first dose (fever due to tumor can be enrolled by investigator);
- (8) Received major surgery or severe trauma, such as cesarean section, thoracotomy, or organ resection through laparoscopic surgery, within 2

months prior to enrollment (surgical incisions should be completely healed before enrollment in this clinical trial);

- (9) Known to have human immunodeficiency virus (HIV) infection or acquired immunodeficiency syndrome (AIDS)-related diseases;
- (10) The presence of interstitial lung disease, non-infectious pneumonia or uncontrolled systemic diseases (e.g., diabetes, hypertension, pulmonary fibrosis and acute pneumonia);
- (11) Untreated active hepatitis (Hepatitis B, defined as HBV-DNA \geq 500 IU/mL; Hepatitis C, defined as HCV-RNA above the detection limit of the assay) or co-infection with hepatitis B and C;
- (12) A known or suspected history of allergy to any relevant drug used in the study;
- (13) Patients who the researchers thought were not suitable for the study.

3.3 Exit criteria:

Participants may withdraw from the trial at any time, or be asked to withdraw by the investigator or sponsor for safety or behavioral reasons or because they are unable to comply with the study visit time or steps required by the protocol. Withdrawal criteria include:

- (1) The subject withdrew the informed consent to participate in the study and refused further follow-up;
- (2) Clinical adverse events, laboratory abnormalities or concurrent diseases occur and the subject considers it not in the best interest of the subject to continue to participate in the study;

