4.1 Study treatment grouping

This study is a prospective, open-label, double-arm, Phase II clinical trial that includes a neoadjuvant treatment group using the mFOLFOX6 regimen and a neoadjuvant treatment group combining the mFOLFOX6 regimen with Citrus Flavonoid Tablets (Aimalang). The study aims to enroll patients with locally advanced rectal cancer who are in clinical stage I, II, or III. Endoscopic biopsy specimens will be collected for YWHAB immunohistochemical testing to identify patients with high YWHAB expression in locally advanced rectal cancer. These patients will then be randomly assigned to either the mFOLFOX6 treatment group or the mFOLFOX6 combined with Citrus Flavonoid Tablets (Aimalang) treatment group for neoadjuvant therapy. The mFOLFOX6 regimen involves 4-6 cycles before surgery and 6-8 cycles after surgery, with each cycle lasting 14 days: on day 1, 85 mg/m² of oxaliplatin is administered intravenously over 180 minutes; on day 1, 400 mg/m² of leucovorin is administered intravenously over 120 minutes; and on day 1, 2400 mg/m² of 5-fluorouracil is administered continuously intravenously for 46 hours. The Citrus Flavonoid Tablets (Aimalang) treatment regimen involves taking 500mg of Citrus Flavonoid Tablets (Aimalang) orally three times daily, with doses given on days 1-14 of each 14-day cycle.

This trial allows for dose adjustments. Patients who experience disease progression during neoadjuvant therapy may stop the study treatment and directly undergo surgery or follow local guidelines. If a patient cannot tolerate the planned 6 cycles of neoadjuvant therapy, early surgery can be considered. Any patient who has received another anticancer regimen before surgery will stop the study treatment and be managed according to local guidelines. The postoperative

treatment for both groups is determined by the investigator, which may include continuing the mFOLFOX6 regimen combined with Citrus Flavonoid Tablets (Aimalang). It is important to note that all patients in the control group are prohibited from taking Citrus Flavonoid Tablets (Aimalang) without authorization during the trial. If a patient needs to take this medication for any reason, they should consult their primary physician, who will decide whether to use an alternative or discontinue the patient's participation in the trial.

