4.2 Dose adjustment of the investigational drug

4.2.1 Protocol for discontinuation or dose adjustment of treatment

During the study treatment, adverse events will be continuously monitored, and participants will be instructed to promptly inform their attending physician of any adverse events. In cases of mild toxicity, if the investigator, after consultation with the medical monitor or sponsor, deems that dose adjustment or delayed administration is beneficial to the participant's safety, the dose may be adjusted or administration may be postponed. If a dose interruption occurs, the resumption of medication can be delayed by up to 14 days to allow the participant to recover from the toxicity. If the participant has not recovered to the study-specified starting dose within 14 days, the trial will be terminated.

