4.2.4 Dose adjustment criteria

Dose adjustments should be made based on the severity and duration of adverse events following the previous treatment cycle, as classified by the NCI CTCAE version 6.0. If severe hematological or liver-related adverse events occur (excluding liver function impairment due to disease progression), the doses of oxaliplatin, 5-FU, and Citrus Flavonoid Tablets (Aimalang) should be reduced simultaneously. If severe diarrhea or mucosal toxicity (excluding vomiting and hair loss) occurs, the doses of 5-FU and Citrus Flavonoid Tablets (Aimalang) should also be reduced simultaneously. See Table 1.3 for details.

Table 1.3 Dose adjustment for selected adverse events

adverse event	Severe disease classification (NCI CTCAE version 6.0)	Study dose adjustment
granulocytopenia	Grade 4 (<0.5 x 10 ⁹ /L)	Reduce the dose level
Febrile granulocytopenia	Grade 3 or above (ANC <1.0 x 10 ⁹ /L, body temperature ≥ 38.5°C)	Reduce the dose level
thrombocytopenia	Grade 3 or above (<50 x 10 ⁹ /L)	Reduce the dose level
Aspartate transferase	Grade 3 or higher (>5 x ULN)	Reduce the dose

		level
Aspartate transferase	Grade 3 or higher ($>5 \times \text{ULN}$)	Reduce the dose level
serum total bilirubin	Grade 3 or higher ($>3 \times \text{ULN}$)	Reduce the dose level

Note: If the severity of an adverse event does not meet the dose reduction criteria, but the time of administration at the beginning of the next treatment cycle is still not in accordance with the administration criteria, and it occurs repeatedly for more than 2 times, the corresponding drug should be reduced by one dose level according to the above requirements.
		

Oxaliplatin can cause characteristic neurotoxic reactions, mainly manifested as sensory nerve disorders. When the above serious adverse events occur, the oxaliplatin dose should be reduced separately, and the standard adjustment is shown in Table 1.4.

Table 1.4 Dose adjustment for cisplatin-related neurotoxicity

Adverse event	Happen	Study dose adjustment of drugs
Grade 1: abnormal or dull sensation, which can completely subside within one week	Any one of them happen	No adjustment required
Grade 2: abnormal or dull sensation, which does not completely subside during the 2 treatment cycles	Any one of them happen	Reduce the dose level
Level 3: Abnormal or dull sensation with associated dysfunction	First time happened	If the next cycle of treatment can be resumed after discontinuation,

		reduce the dose level by 1

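### Minor: Table 1.1 withholds every next cycle below haemoglobin 90 g/L, but no haemoglobin limit applies at entry or at cycle 1, so a patient known to be below 90 g/L can be randomised and dosed

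*Combined protocol and SAP*

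**What the plan says.** Section 4.2.2 governs re-dosing: "The study drug can be administered only after the results of the examination on the first day before the next treatment cycle confirm". What must be confirmed is that each Table 1.1 criterion holds. The first row is haemoglobin of at least 90 g/L.

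Entry is governed by 3.1(7), which opens "Based on the following laboratory test values obtained during the screening period, appropriate organ function is present" and then gives limits for white cells, neutrophils, platelets, bilirubin, AST or ALT, and creatinine. Haemoglobin is not among them. Among the exclusion criteria, 3.2(3) covers active bleeding where emergency surgery is needed, and 3.2(13) is a general discretion: "Patients who the researchers thought were not suitable for the study".

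Section 5.1 includes haemoglobin in the blood count taken within 7 days before study drug starts. Section 5.2 lists the same count before each administration, and accepts baseline bloods from the previous seven days for the first day of cycle 1. Neither section attaches a haemoglobin cut-off.

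**The concern.** The plan treats haemoglobin below 90 g/L as too low to give study drug at any later cycle, yet lets a patient with such a value, already on record from screening, enter and receive the first cycle. At stake is a small matter of patient safety and consistency. Such a patient is exposed once at a level the plan would not accept two weeks later, and is then held at cycle 2 unless the value has risen. Two investigators can also decide differently about the same patient, because the only general barrier at entry is judgement without a number.

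The population makes the case plausible. Every participant has rectal adenocarcinoma, and 3.1(1) as written also asks for signs of haemorrhoids. That both can cause blood loss is general clinical knowledge; the plan gives no figure for how often haemoglobin is low at screening.

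**Working it through.** There is no stated figure to reproduce, and no sample size or power formula applies. The check is a comparison of the entry limits with the next-cycle limits.

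| Value | Entry, 3.1(7) | Next cycle, Table 1.1 | Stricter side |
|---|---|---|---|
| Haemoglobin | no limit | ≥ 90 g/L | next cycle |
| Neutrophils | ≥ 1.5 × 10⁹/L | ≥ 1.5 × 10⁹/L | same |
| Platelets | ≥ 75 × 10⁹/L | ≥ 75 × 10⁹/L | same |
| Total bilirubin | ≤ 1.5 × UNL | ≤ 1.5 × UNL | same |
| Creatinine | ≤ 1.5 × UNL | ≤ 1.5 × UNL | same |
| AST | ≤ 2.5 × UNL (AST or ALT) | ≤ 3 × UNL | entry, if both must comply |
| ALT | ≤ 2.5 × UNL (AST or ALT) | ≤ 3 × UNL | entry, if both must comply |
| White cells | ≥ 3 × 10⁹/L | no limit | entry |

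1. Table 1.1 has 7 laboratory rows. Four match the entry limits, two (AST, ALT) are stricter at entry on the reading shown, and one (haemoglobin) has no entry limit: 4 + 2 + 1 = 7.
2. The white-cell mismatch runs the other way. Entry is the stricter side, so it cannot admit a patient whom the next-cycle rule would then hold.
3. Does anything else stop cycle 1? Criterion 3.2(3) reaches only bleeding that needs emergency surgery. Criterion 3.2(13) is discretionary. Sections 5.1 and 5.2 require the measurement but set no threshold.
4. Does Table 1.1 itself apply to cycle 1? The section heading, the table title and the quoted sentence all refer to the next cycle, and the diarrhoea row is judged against baseline. The natural reading is cycles after the first.
5. How often does the rule apply before surgery? With 4 to 6 planned preoperative cycles, it applies at 4 − 1 = 3 to 6 − 1 = 5 cycle starts. Cycle 1 is the one start it does not cover.

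**The case against.** The strongest reply is that entry criteria and re-dosing criteria do different jobs and need not match. A number at re-dosing with judgement at entry is a coherent choice, and the investigator has the haemoglobin result before cycle 1 and may decline the patient under 3.2(13). It stands that the lists need not mirror each other and that discretion exists. It does not remove the gap. The plan chose numbers at entry for the other Table 1.1 laboratory values, gives no reason for leaving haemoglobin out, and leaves the outcome to vary between investigators.

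A second reply is that later provisions deal with such a patient. Section 4.1 says: "If a patient cannot tolerate the planned 6 cycles of neoadjuvant therapy, early surgery can be considered". Criterion 3.3(2) allows withdrawal, and section 4.3.1 restricts anti-tumour treatment, so correcting anaemia is not prohibited. All true, but these act after cycle 1 has been given.

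A third reply is that Table 1.1 could be stretched to cover cycle 1. On that reading the patient could still be randomised and then not dosed, which leaves a patient in the ITT set but outside the full analysis set as section 8.1 defines it. An entry limit is the cleaner remedy either way.

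A reader might go further and infer that the 14-day rule in 4.2.1 would end treatment for this patient. The documents do not support building on that. The rule allows that "the resumption of medication can be delayed by up to 14 days to allow the participant to recover from the toxicity", and stable anaemia present before any study drug is not naturally toxicity. The text does not say so expressly, but that is a drafting detail and not part of this point.

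**Conclusion.** The gap is real and minor. A patient with a known screening haemoglobin below 90 g/L satisfies every numeric entry rule, can be randomised and given cycle 1, and is then held at cycle 2 unless the value is corrected. How many patients this affects cannot be estimated from the documents.

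Two readings carry the conclusion: that Table 1.1 applies from cycle 2 onward, and, for the statement that the other six rows are at least as strict at entry, that 3.1(7) requires both transaminases to comply. Read literally, one would be enough: a patient with AST at 2 × UNL and ALT at 4 × UNL could enter and then fail the ALT row. Haemoglobin should therefore not be called the sole looser row without that qualification.

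A reader might also infer that held or shortened treatment distorts the downstaging comparison or costs power. The documents do not support this. The same entry and re-dosing rules apply to both arms, and nothing in the plan says how many patients would be held or for how long.

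**What to change.** Add haemoglobin of at least 90 g/L to 3.1(7), judged on a screening blood count whose result is available before randomisation. Say expressly that correction and a repeat count are allowed within the 28-day screening window of section 5.1. The timing needs to be stated because the existing 7-day blood count is tied to the start of study drug, and the plan does not say that randomisation follows it.

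The cost is a short wording amendment, one repeat blood count for each patient found below 90 g/L, possibly a short delay for those patients, and non-enrolment of those who cannot be corrected in time. That last number cannot be estimated from the documents.

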4.2.3 Study drug dose levels

If a reduction in drug dosage is required in medical practice, the dose levels of oxaliplatin and 5-fluorouracil can be adjusted according to the criteria listed in Table 1.2. Each adjustment should only reduce one dose level, and the total number of dose level adjustments throughout the study period should not exceed two. The fixed dose of suberythrocitin is 400 mg/m² or 7.5 mg/kg (for the 3-week regimen). All dose level adjustments must be clearly documented with the reasons for the adjustment.

Table 1.2 Study drug dose levels

Name of drug	Initial dose (mg/m ²)	Dose level-1 (mg/m ²)	Dose level-2 (mg/m ²)
oxaliplatin	85	65	50
5-FU	2400	2300	2200
Citrus flavonoid tablets (Aimalang)	Take orally, 500mg Tid	Take orally, 500mg twice daily	Take orally, 500mg Qd

4.2.4 Dose adjustment criteria

Dose adjustments should be made based on the severity and duration of adverse events following the previous treatment cycle, as classified by the NCI CTCAE version 6.0. If severe hematological or liver-related adverse events occur (excluding liver function impairment due to disease progression), the doses of oxaliplatin, 5-FU, and Citrus Flavonoid Tablets (Aimalang) should be reduced simultaneously. If severe diarrhea or mucosal toxicity (excluding vomiting and hair loss) occurs, the doses of 5-FU and Citrus Flavonoid Tablets (Aimalang) should also be reduced simultaneously. See Table 1.3 for details.

Table 1.3 Dose adjustment for selected adverse events

adverse event	Severe disease classification (NCI CTCAE version 6.0)	Study dose adjustment
granulocytopenia	Grade 4 (<0.5 x 10 ⁹ /L)	Reduce the dose level
Febrile granulocytopenia	Grade 3 or above (ANC <1.0 x 10 ⁹ /L, body temperature ≥ 38.5°C)	Reduce the dose level
thrombocytopenia	Grade 3 or above (<50 x 10 ⁹ /L)	Reduce the dose level
Aspartate transferase	Grade 3 or higher (>5 x ULN)	Reduce the dose

		level
Aspartate transferase	Grade 3 or higher ($>5 \times \text{ULN}$)	Reduce the dose level
serum total bilirubin	Grade 3 or higher ($>3 \times \text{ULN}$)	Reduce the dose level

Note: If the severity of an adverse event does not meet the dose reduction criteria, but the time of administration at the beginning of the next treatment cycle is still not in accordance with the administration criteria, and it occurs repeatedly for more than 2 times, the corresponding drug should be reduced by one dose level according to the above requirements.
		

Oxaliplatin can cause characteristic neurotoxic reactions, mainly manifested as sensory nerve disorders. When the above serious adverse events occur, the oxaliplatin dose should be reduced separately, and the standard adjustment is shown in Table 1.4.

Table 1.4 Dose adjustment for cisplatin-related neurotoxicity

Adverse event	Happen	Study dose adjustment of drugs
Grade 1: abnormal or dull sensation, which can completely subside within one week	Any one of them happen	No adjustment required
Grade 2: abnormal or dull sensation, which does not completely subside during the 2 treatment cycles	Any one of them happen	Reduce the dose level
Level 3: Abnormal or dull sensation with associated dysfunction	First time happened	If the next cycle of treatment can be resumed after discontinuation,

		reduce the dose level by 1
	The reaction failed to recover to grade 2 after discontinuation of the drug	Permanent discontinuation of medication

4.3 Combination and concomitant drugs

4.3.1 Prohibited combination and concomitant drugs

No other anti-tumor treatment is allowed during the study, including: chemotherapy, molecular targeted therapy, hormone therapy, immunotherapy, biological therapy, non-palliative radiotherapy and immunomodulators (including but not limited to: interferon, interleukin-2, etc.).

4.3.2 Other anti-tumor treatment and experimental drugs

During the study treatment, the subject will not be allowed to receive other anti-tumor treatments not specifically specified in this protocol. Other systemic anti-tumor treatments will not be allowed.

5. Research process

5.1, Screening period

After the patient signs the informed consent form, they enter the screening phase. Endoscopic biopsy specimens from patients with locally advanced rectal cancer are collected for YWHAB immunohistochemical testing to identify those with high YWHAB expression, and these patients are selected for inclusion in the study. Before signing the informed consent, patients undergo routine laboratory tests and imaging assessments as required by clinical practice. If the relevant data is available within the specified time window, it can be utilized.

The following screening should be completed within 28 days prior to the start of study drug therapy:

- Obtain informed consent signed by the subject;

- Collect demographic data: name, sex, date of birth, height, weight, etc.;
- Collect adverse events: record adverse events from the time of signing informed consent;
- Tumor diagnosis: date of pathological confirmation, pathological grading, clinical imaging staging (TNM), clinical staging, etc.;
- History of cancer treatment;
- Imaging examination: enhanced CT of chest, abdomen and pelvis;
- The YWHAB immunohistochemical detection was performed on the endoscopic biopsy specimens.
- (Non-essential) Specify the KRAS exon 2 codons 12 and 13, exon 3 codons 59 and 61, exon 4 codons 117 and 146, NRAS exon 2 codons 12 and 13, exon 3 codons 59 and 61, exon 4 codons 117 and 146, and BRAF V600E gene status;
- (Mandatory) MMR/MSI detection of tumor tissue;
- The following screening should be completed within 7 days prior to the start of study drug therapy:
 - Weight and ECOG score;
 - Life signs: pulse, respiratory rate, body temperature and blood pressure;
 - Comprehensive physical examination: general condition, head and face, skin, lymph nodes, eyes, ear, nose and throat, oral cavity, respiratory system, cardiovascular system, abdomen, reproductive and urinary system, musculoskeletal, nervous system and mental state;
 - Complete blood count: red blood cell count, hemoglobin, platelet count, white blood cell count, neutrophil count and lymphocyte classification count;
 - Routine urine: white blood cells, red blood cells, protein in urine; if protein in urine is greater than or equal to 2+, 24-hour urine protein quantification should be added;
 - Blood biochemical: ALT, AST, γ -GT, TBIL, DBIL, AKP, BUN or urea (preferably BUN), TP, ALB, Cr, GLU, K+, Na+, Ca2+, Mg2+, Cl-;

- Tumor markers;
- Coagulation function: activated partial thromboplastin time (APTT), prothrombin time (PT), thrombin time (TT), fibrinogen (FIB), international normalized ratio (INR);
- 12. Lead electrocardiogram: attention should be paid to QT, QTc and P-R intervals. If there are abnormalities, other relevant tests should be done according to the investigator's judgment;
- Echocardiography: at least the assessment of left ventricular ejection fraction (LVEF) should be included;
- Pregnancy test: suitable for women of childbearing age, using serum pregnancy test.

5.2, treatment period

The treatment period begins with the first dose of the study drug and ends when the study treatment is discontinued. The first study medication should be administered as close as possible to the completion of the screening period to confirm eligibility. All examinations and assessments, except for imaging studies, should be completed within three days before the first dose. For the laboratory tests (complete blood count, urinalysis, fecal occult blood test, biochemical blood tests, coagulation function, and thyroid function) and electrocardiogram on the first day of the first cycle, if baseline laboratory tests were conducted within seven days before the first dose, they do not need to be repeated.

The following assessments should be completed prior to each study treatment administration:

- Weight and ECOG score;
- vital sign ;
- check-up ;
- Complete blood count: red blood cell count, hemoglobin, platelet count, white blood cell count, neutrophil count and lymphocyte classification

count;

- Blood biochemical: ALT, AST, γ -GT, TBIL, DBIL, AKP, BUN or urea (preferably BUN), TP, ALB, Cr, GLU, K+, Na+, Ca2+, Mg2+, Cl-;
- Routine urine: white blood cells, red blood cells, protein in urine; if protein in urine is greater than or equal to 2+, 24-hour urine protein quantification should be added;
- Coagulation function: activated partial thromboplastin time (APTT), prothrombin time (PT), thrombin time (TT), fibrinogen (FIB), international normalized ratio (INR);
- Tumor markers;
- 12. Lead electrocardiogram: attention should be paid to QT, QTc and P-R intervals. If there are abnormalities, other relevant tests should be done according to the investigator's judgment;
- Document adverse events;
- Imaging evaluation: Imaging evaluation was performed after 6 cycles and 12 cycles of mFOLFOX6 regimen adjuvant chemotherapy, including chest, abdominal and pelvic enhanced CT and pelvic MRI. Any subject suspected of disease progression during treatment (e.g., symptom deterioration) could undergo unplanned imaging evaluation.

